10.1.2 Serious adverse events

An SAE is defined as any adverse event [appearance of (or worsening of any pre-existing)] undesirable sign(s), symptom(s), or medical conditions(s) which meets any one of the following criteria:

- fatal
- life-threatening

Life-threatening in the context of a SAE refers to a reaction in which the participant was at risk of death at the time of the reaction; it does not refer to a reaction that hypothetically might have caused death if it were more severe (please refer to the ICH-E2D Guidelines).

- results in persistent or significant disability/incapacity
- constitutes a congenital anomaly/birth defect
- requires inpatient hospitalization or prolongation of existing hospitalization, unless hospitalization is for:
 - routine treatment or monitoring of the studied indication, not associated with any deterioration in condition
 - elective or pre-planned treatment for a pre-existing condition that is unrelated to the indication under study and has not worsened since signing the informed consent
 - social reasons and respite care in the absence of any deterioration in the participant's general condition
 - treatment on an emergency outpatient basis for an event not fulfilling any of the definitions of a SAE given above and not resulting in hospital admission
- is medically significant, e.g. defined as an event that jeopardizes the participant or may require medical or surgical intervention to prevent one of the outcomes listed above

Medical and scientific judgment should be exercised in deciding whether other situations should be considered serious reactions, such as important medical events that might not be immediately life threatening or result in death or hospitalization but might jeopardize the participant or might require intervention to prevent one of the other outcomes listed above. Such events should be considered as "medically significant." Examples of such events are intensive treatment in an emergency room or at home for allergic bronchospasm, blood dyscrasias, or convulsions that do not result in hospitalization or development of dependency or abuse (please refer to the ICH-E2D Guidelines).

All new malignant neoplasms will be assessed as serious under "medically significant" if other seriousness criteria are not met.

Any suspected transmission via a medicinal product of an infectious agent is also considered a serious adverse reaction.

All reports of intentional misuse and abuse of the product are also considered serious adverse event irrespective if a clinical event has occurred.

10.1.3 SAE reporting

To ensure participant safety, every SAE, regardless of causality, occurring after the participant has provided informed consent and until 30 days after the last study visit must be reported to

Novartis safety immediately, without undue delay but not later than within 24 hours of learning of its occurrence. Detailed instructions regarding the submission process and requirements are to be found in the investigator folder provided to each site.

All follow-up information for the SAE including information on complications, progression of the initial SAE and recurrent episodes must be reported as follow-up to the original episode immediately, without undue delay but not later than within 24 hours of the investigator receiving the follow-up information. An SAE occurring at a different time interval or otherwise considered completely unrelated to a previously reported one must be reported separately as a new event.

If the SAE is not previously documented in the Investigator's Brochure or Package Insert (new occurrence) and is thought to be related to the study treatment, a CMO & PS Department associate may urgently require further information from the investigator for health authority reporting. Novartis may need to issue an Investigator Notification (IN) to inform all investigators involved in any study with the same study treatment that this SAE has been reported.

Every SAE occurring to a subject after completion of the clinical trial has to be reported to the sponsor by the investigator if it is suspected to be causally related to the investigation product.

Suspected Unexpected Serious Adverse Reactions (SUSARs) will be collected and reported to the competent authorities and relevant ethics committees in accordance with EU Guidance 2011/C 172/01 or as per national regulatory requirements in participating countries.

10.1.4 Pregnancy reporting

Pregnancies

If a female trial participant becomes pregnant, the study treatment should be stopped, and the trial participant must be asked to read and sign pregnancy consent form to allow the Study Doctor ask about her pregnancy. To ensure participant safety, each pregnancy occurring after signing the informed consent must be reported to Novartis within 24 hours of learning of its occurrence. The pregnancy should be followed up to determine outcome, including spontaneous or voluntary termination, details of the birth, and the presence or absence of any birth defects, congenital abnormalities, or maternal and/or newborn complications.

Pregnancy should be recorded and reported by the investigator to the Novartis Chief Medical Office and Patient Safety (CMO&PS). Pregnancy follow-up should be recorded on the same form and should include an assessment of the possible relationship to the investigational study treatmentany pregnancy outcome. Any SAE experienced during pregnancy must be reported.

10.1.5 Reporting of study treatment errors including misuse/abuse

Medication errors are unintentional errors in the prescribing, dispensing, administration or monitoring of a medicine while under the control of a healthcare professional, participant or consumer (EMA definition).

Misuse refers to situations where the medicinal product is intentionally and inappropriately used not in accordance with the protocol.

Abuse corresponds to the persistent or sporadic, intentional excessive use of a medicinal product, which is accompanied by harmful physical or psychological effects.

Study treatment errors and uses outside of what is foreseen in the protocol will be recorded on the appropriate CRF irrespective of whether or not associated with an AE/SAE and reported to Safety only if associated with an SAE. Misuse or abuse will be collected and reported in the safety database irrespective of it being associated with an AE/SAE within 24 hours of Investigator's awareness.

Table 10-1 Guidance for capturing the study treatment errors including misuse/abuse

Treatment error type	Document in Dosing CRF (Yes/No)	Document in AE eCRF	Complete SAE form
Unintentional study treatment error	Yes	Only if associated with an AE	Only if associated with an SAE
Misuse/Abuse	Yes	Yes	Yes, even if not associated with a SAE

For more information on AE and SAE definition and reporting requirements, please see the respective sections.

11 Data Collection and Database management

11.1 Data collection

Designated investigator staff will enter the data required by the protocol into the Electronic Case Report Forms (eCRF). The eCRFs have been built using fully validated secure web-enabled software that conforms to 21 CFR Part 11 requirements, Investigator site staff will not be given access to the EDC system until they have been trained. Automatic validation programs check for data discrepancies in the eCRFs, allow modification and/or verification of the entered data by the investigator staff.

The investigator/designee is responsible for assuring that the data (recorded on CRFs) (entered into eCRF) is complete, accurate, and that entry and updates are performed in a timely manner. The Investigator must certify that the data entered are complete and accurate.

After final database lock, the investigator will receive copies of the participant data for archiving at the investigational site.

All data should be recorded, handled, and stored in a way that allows its accurate reporting, interpretation, and verification.

11.2 Database management and quality control

Novartis personnel (or designated CRO) will review the data entered by investigational staff for completeness and accuracy. Electronic data queries stating the nature of the problem and requesting clarification will be created for discrepancies and missing values and sent to the

investigational site via the EDC system. Designated investigator site staff are required to respond promptly to queries and to make any necessary changes to the data.

Concomitant treatments and prior medications entered into the database will be coded using the World Health Organization (WHO) Drug Reference List, which employs the Anatomical Therapeutic Chemical classification system. Medical history/current medical conditions and adverse events will be coded using the Medical Dictionary for Regulatory Activities (MedDRA) terminology.

11.3 Site monitoring

Before study initiation, at a site initiation visit or at an investigator's meeting, a Novartis representative will review the protocol and data capture requirements (i.e. eSource DDE or eCRFs) with the investigators and their staff. During the study, Novartis employs will apply several methods of ensuring protocol and GCP compliance and the quality/integrity of the sites' data. The field monitor will visit the site to check the completeness of participant records, the accuracy of data capture / data entry, the adherence to the protocol and to Good Clinical Practice, the progress of enrollment. For this clinical trial, it will specifically be verified that patients have received a permitted SARS-CoV-2 mRNA vaccine during initial vaccination cycle by checking the patient's vaccination certificate. As this study aims at resembling the clinical routine as closely as possible, field monitors will confirm the patients' treatment adherence during on site monitoring visits by verifying the continuous prescription of the respective MS drug (prescription records or equivalent sources). Key study personnel must be available to assist the field monitor during these visits. Additionally, a central analytics organization may analyze data & identify risks & trends for site operational parameters, and provide reports to Novartis clinical teams to assist with trial oversight.

The investigator must maintain source documents for each participant in the study, consisting of case and visit notes (hospital or clinic medical records) containing demographic and medical information, laboratory data, electrocardiograms, and the results of any other tests or assessments. All information on CRFs must be traceable to these source documents in the participant's file. The investigator must also keep the original informed consent form signed by the participant (a signed copy is given to the participant).

The investigator must give the monitor access to all relevant source documents to confirm their consistency with the data capture and/or data entry. Novartis monitoring standards require full verification for the presence of informed consent, adherence to the inclusion/exclusion criteria, documentation of SAEs, and of data that will be used for all primary variables. Additional checks of the consistency of the source data with the CRFs are performed according to the study-specific monitoring plan. No information in source documents about the identity of the participants will be disclosed.

12 Data analysis and statistical methods

Any data analysis carried out independently by the investigator should be submitted to Novartis before publication or presentation.

12.1 Analysis sets

For all analysis sets, participants will be analyzed according to the study treatment(s) received. The safety analysis set will include all participants that received any study drug.

The efficacy analysis sets at one week, one month and six month and additionally after a potential booster vaccination respectively will include all participants who have a valid determination of functional antibodies to SARS-CoV-2 at that time point plus those who failed to receive their second dose of vaccine for whatever reason. The latter will be counted as non-responders. Patients completing vaccination but fail to provide a blood sample at one week after the second vaccination will be excluded from the study and analysis.

12.2 Participant demographics and other baseline characteristics

Demographic and other baseline data including disease characteristics will be listed and summarized descriptively by treatment group (Cohort 1-3) for the FAS.

The Safety set will be used for the analyses below. Categorical data will be summarized as frequencies and percentages. For continuous data, mean, standard deviation, median, minimum, and maximum will be presented.

For Cohort 1, the continued siponimod intake after vaccination will be presented. For Cohort 2 the duration of discontinuation (time between last prior to vaccination and first dose after vaccination will be summarized. For Cohort 3, the various base DMTs will be summarized (type, doses and duration) as appropriate.

Concomitant medications and significant non-drug therapies prior to and after the start of the study treatment will be listed and summarized according to the Anatomical Therapeutic Chemical (ATC) classification system, by cohort.

12.3 Analysis of the primary endpoint

The primary clinical question in this trial is: what is the proportion of SPMS patients treated with siponimod within the tree cohorts defined below which mount an immune response to a SARS-CoV-2 modRNA vaccine?

12.3.1 Definition of primary endpoint(s)/estimand(s)

The primary endpoint of the study is the proportion of participants achieving seroconversion as defined by detection of SARS-CoV-2 serum functional antibodies one week after second dose of vaccine in participants treated concomitantly with siponimod and siponimod treatment break (yes/no).

12.3.2 Statistical model, hypothesis, and method of analysis

The primary analysis will not use any statistical testing or modelling. The absolute numbers and the proportion of participants achieving seroconversion within each cohort will be calculated. It will be augmented by a (descriptive) 95% confidence interval (exact Clopper-Pearson).

12.3.3 Handling of remaining intercurrent events of primary estimand

Patients who fail to receive their second dose of vaccine for whatever reason will be included in the analysis as non-responders. Patients who did receive their second dose of vaccine and do not have a valid determination of functional antibodies to SARS-CoV-2 for whatever reason will be excluded from the analysis of vaccine efficacy.

12.3.4 Supportive analyses

Patient demographics and baseline characteristics among 3 cohorts will be compared in the data analysis. Also the treatment interruption time of the selected cohort 2 patients will be compared to that of other siponimod treated patients in AMASIA interrupting daily dosing as per label for the purpose of vaccination with SARS-CoV-2 modRNA as part of clinical routine. If major imbalance is discovered, the study results will be interpreted with more caution and post-hoc supportive analyses may be conducted to adjust for the imbalance.

12.4 Analysis of secondary endpoints

All secondary endpoints will be summarized descriptively as frequencies and percentages, or, for continuous data, mean, standard deviation, median, minimum, and maximum will be presented.

12.4.1 Safety endpoints

For all safety analyses, the safety set will be used. All listings and tables will be presented by cohort.

Safety summaries (tables, figures) include only data from the on-treatment period which will also be summarized where appropriate (e.g. change from baseline summaries). In addition, a separate summary for death including on treatment and post treatment deaths will be provided. In particular, summary tables for adverse events (AEs) will summarize only on-treatment events, with a start date during the on-treatment period (treatment-emergent AEs).

The on-treatment period lasts from the date of first administration of study treatment to 30 days after the month 12 COVID-19 follow-up call.

Adverse events

All information obtained on adverse events will be displayed by cohort.

The number (and percentage) of participants with treatment emergent adverse events (events started after the first dose of study medication or events present prior to start of double-blind treatment but increased in severity based on preferred term) will be summarized in the following ways:

- by cohort, primary system organ class and preferred term.
- by treatment, primary system organ class, preferred term and maximum severity.

Separate summaries will be provided for study medication related adverse events, death, serious adverse events, other significant adverse events leading to discontinuation, and adverse events leading to dose adjustment.

A participant with multiple adverse events within a primary system organ class is only counted once towards the total of the primary system organ class.

Vital signs

All vital signs data will be listed by treatment group, participant, and visit/time and if ranges are available, abnormalities (and relevant orthostatic changes) will be flagged. Summary statistics will be provided by treatment and visit/time.

Clinical laboratory evaluations

All laboratory data will be listed by treatment group (cohort 1-3), participant, and visit/time and if normal ranges are available abnormalities will be flagged. Summary statistics will be provided by treatment and visit/time.

12.5 Interim analyses

An interim analysis will be performed when all participants have completed study visit 1 (one week after SARS-CoV-2 vaccination cycle completion) as this reflects the primary endpoint. As all analyses in this study are purely descriptive, there is no need for any statistical adjustments. Additional interim analyses may be conducted to support decision making concerning the current clinical study including an increase in participants (from 60 to 90), the sponsor's clinical development projects in general, or in case of any safety concerns.

12.6 Sample size calculation

12.6.1 Primary endpoint(s)

The sample size of 20 participants per arm is selected based on need for early availability of results for the current covid-19 pandemic and the feasibility to recruit sufficient participants from AMASIA and PANGAEA 2.0 EVOLUTION. This sample size of 20 subjects will provide estimates of proportion responded with margin of error (half-width of a 95% confidence interval) of 20.1%, 19%, and 17.5% corresponding to response rates of 70%, 75%, and 80%, respectively. Adjusting for 10% drop-out, 22 subjects will be enrolled in each arm. In case of fast recruitment the sponsor is allowed to increase sample size in each arm by up to 10 additional patients to support the generation of meaningful data in a larger sample size.

13 Ethical considerations and administrative procedures

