Efficacy assessments	
Detection of SARS-CoV-2 serum functional antibodiesDetection of SARS-CoV-2 specific T-cells
Key safety assessments	
Patients developing COVID-19
Data analysis	The primary analysis will not use any statistical testing or modelling. The absolute numbers and the proportion of participants achieving seroconversion within each cohort will be calculated. It will be augmented by a (descriptive) 95% confidence interval (exact Clopper-Pearson). All secondary endpoints will be summarized descriptively as frequencies and percentages, or, for continuous data, mean, standard deviation, median, minimum, and maximum will be presented.
Key words	COVID-19, SARS-CoV-2, RNA vaccine, siponimod, secondary progressive multiple sclerosis

1 Introduction

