This is a three cohort, multicenter, open-label, prospective study of 60 (optional increase to 90) MS patients currently treated with siponimod or a first-line DMT (as per EU SmPC) or without MS treatment planning to undergo a SARS-CoV-2 modRNA vaccination as part of clinical routine and according to the respective EU SmPC. For each participant, total expected duration of the trial is 56-60 weeks.

- The first cohort will be participants not interrupting their current siponimod therapy for the purpose of a SARS-CoV-2 modRNA vaccination. In case of a booster vaccination, patients in this cohort may also undergo a treatment break which is also covered by the EU SmPC.
- The second cohort will be participants interrupting their current siponimod therapy for the purpose of a SARS-CoV-2 modRNA vaccination (treatment interruption of about 2-3 months).

- The third cohort will be participants receiving modRNA vaccine while on treatment with first-line DMTs (dimethylfumarate, glatirameracetate, interferons, teriflunomide) or no current treatment in clinical routine.

The interventional part of AMA-VACC is limited to the collection of blood samples at specified time-points to analyze levels of SARS-CoV-2 specific antibodies and T-cells as response to the modRNA vaccination in clinical routine.

There are 3 study periods:

1. Screening period:

Participants enter a screening period of up to 1 month to assess eligibility requirements including a blood draw and assessment of SARS-CoV-2 specific antibodies at baseline to exclude any prior exposure to the virus or a vaccination. In case the patient is not eligible for SARS-CoV-2 vaccination by local regulation within this time, the Novartis Medical Advisor should be contacted to discuss further proceeding including re-evaluation of anti-SARS-CoV-2 antibody level and PCR test. Furthermore, a SARS-CoV-2 PCR test will be performed at screening to exclude current COVID-19 infection. In case of a positive test result, the patient has to go into quarantine immediately. Patients are only allowed to continue within the study and receive SARS-CoV-2 vaccination once they received a negative PCR test result.

2. Vaccination period

Patients are vaccinated with a complete cycle of modRNA based SARS-CoV-2 vaccine at the discretion of the treating physician outside the study as part of clinical routine.

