4.5.1 Blood sample volume

A volume smaller than a typical blood donation is planned to be collected over a period of up to 9 months, from each participant as part of the study. Additional samples may be required for safety monitoring.

Timings of blood sample collection are outlined in the assessment schedule (Table 8-1).

A summary blood log is provided in the laboratory manual. Instructions for sample collection, processing, storage and shipment information are also available in the laboratory manual.

Blood samples will be stored until the end of the study in case measurements need to be repeated.

5 Study Population

The study population will consist of 60 (optional increase to 90 after first interim analysis) females and males at risk for SPMS or with SPMS diagnosis treated in clinical routine with either siponimod, a first line MS DMT or no current therapy.

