### 1.1 Study design

This is a three-cohort, multicenter, open-label, prospective study of 60 patients suffering from multiple sclerosis (MS) currently treated with siponimod or a first-line disease modifying drug (DMT) or without MS treatment planning to undergo a SARS-CoV-2 modRNA vaccination as part of clinical routine and according to the respective SmPC.

MS treatments as part of clinical routine:

- Cohort 1: Siponimod treatment according to EU SmPC without interrupting daily dosing for the purpose of vaccination with SARS-CoV-2 modRNA
- Cohort 2: Siponimod treatment according to EU SmPC interrupting daily dosing for the purpose of vaccination with SARS-CoV-2 modRNA
- Cohort 3: Dimethylfumarate, glatirameracetate, interferon, teriflunomode as per respective EU SmPC or no current treatment with diagnosis of SPMS or with RRMS at risk to develop SPMS (at the discretion of the treating physician)

An interim analysis is planned after all participants have completed the study at one week after the end of the SARS-CoV-2 vaccination cycle in the study. The week +1 data regarding antibody and T-cell response (along with relevant safety data) will be examined as a preliminary evaluation of proof of concept and are the basis for the primary endpoint of the study.

The primary analysis time point is when all participants have completed the study visit 6 months after the end of the SARS-CoV-2 vaccination cycle in the study.

A follow-up analysis is planned after all participants have completed the follow-up visit 12 months.

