## 2.5.2 Statistical hypothesis, model, and method of analysis

The efficacy analysis set at Week 1 is used for all analyses of the primary parameter.

The primary analysis will not use any statistical testing or modelling. The absolute numbers and the proportion of participants achieving seroconversion within each cohort will be calculated. It will be augmented by a (descriptive) two-sided 95% confidence interval (exact Clopper-Pearson).

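### The 95% CI half-widths quoted for 20 per cohort are normal-approximation (Wald) values; the planned exact Clopper-Pearson interval is wider by 1.1 to 1.5 points

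*Protocol*

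**What the plan says.** The precision statement is the same in Protocol 12.6.1 and SAP section 3. It is tied to 20 participants: "This sample size of 20 subjects will provide estimates of proportion responded with margin of error". The figures are a "margin of error (half-width of a 95% confidence interval) of 20.1%, 19%, and 17.5% corresponding to response rates of 70%, 75%, and 80" per cent. No interval method is named. Both sections base the choice of 20 on the need for early results and on feasible recruitment.

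The interval to be reported is named elsewhere. Protocol 12.3.2, like the Data analysis row of the Protocol summary, says of the seroconversion proportion: "It will be augmented by a (descriptive) 95% confidence interval (exact Clopper-Pearson"). SAP 2.5.2 has it "augmented by a (descriptive) two-sided 95% confidence interval (exact Clopper-Pearson"). No other interval is planned for this proportion.

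On numbers of participants, Protocol section 3 describes a "prospective study of 60 (optional increase to 90"), Protocol section 5 states "The study population will consist of 60 (optional increase to 90 after first interim analysis"), and SAP 1.1 describes a "prospective study of 60 patients suffering from multiple sclerosis (MS"). Protocol 12.6.1 and SAP section 3 add: "Adjusting for 10% drop-out, 22 subjects will be enrolled in each arm".

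**The concern.** A precision statement should describe the interval that the study will report. At n = 20 and response rates of 70% to 80%, the exact interval is wider than the Wald interval and clearly asymmetric, so a single Wald margin misdescribes it in two ways. It understates the width, and it hides the fact that the lower limit lies further from the estimate than the upper limit does.

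The half-widths are the only quantitative statement in either document of what 20 per cohort provides. The study asks whether siponimod-treated patients can mount a response at all (Protocol 4.1), so readers will look mainly at the lower limit, which is where the stated margin is most optimistic.

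**Working it through.** **Inputs.** n = 20 per cohort, confidence level 95%, response rates 70%, 75% and 80% (Protocol 12.6.1, SAP section 3). These rates correspond to 14, 15 and 16 responders. Method to be reported: two-sided exact Clopper-Pearson (Protocol 12.3.2, SAP 2.5.2).

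**Step 1: reproduce the plan's figures.** The Wald half-width is 1.96·√(p(1−p)/n).

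- p = 0.70: 1.96·√(0.21/20) = 20.08%, stated 20.1%
- p = 0.75: 1.96·√(0.1875/20) = 18.98%, stated 19%
- p = 0.80: 1.96·√(0.16/20) = 17.53%, stated 17.5%

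All three match. The alternatives tried at n = 20 do not: Wald with continuity correction (22.6, 21.5, 20.0), t-based (21.4, 20.3, 18.7), Wilson (18.7, 17.8, 16.8), Agresti-Coull (18.9, 18.2, 17.3) and Jeffreys (19.1, 18.1, 16.8). Wald at n = 22 (19.2, 18.1, 16.7) does not match either.

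**Step 2: the planned interval.** For x responders out of n, the lower limit is the 2.5% quantile of Beta(x, n−x+1) and the upper limit is the 97.5% quantile of Beta(x+1, n−x). The half-width is (upper − lower)/2.

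| Responders | Exact 95% limits | Half-width | Stated | Shortfall | Distance below / above estimate |
|---|---|---|---|---|---|
| 14/20 (70%) | 45.72–88.11% | 21.19 | 20.1 | 1.09 | 24.3 / 18.1 |
| 15/20 (75%) | 50.90–91.34% | 20.22 | 19 | 1.22 | 24.1 / 16.3 |
| 16/20 (80%) | 56.34–94.27% | 18.96 | 17.5 | 1.46 | 23.7 / 14.3 |

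As a share of the stated value, the shortfall is 1.09/20.1 = 5%, 1.22/19 = 6% and 1.46/17.5 = 8%.

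The lower limits implied by the stated margins are 70 − 20.1 = 49.9%, 75 − 19 = 56.0% and 80 − 17.5 = 62.5%. The exact lower limits are 45.7%, 50.9% and 56.3%, which are 4.2, 5.1 and 6.2 points lower.

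**Step 3: a second reading of the response rate.** If 70%, 75% and 80% are true rates and not observed ones, the comparable quantity is the expected Clopper-Pearson half-width over the binomial distribution at n = 20. It is 20.65, 19.65 and 18.36. The shortfall falls to 0.55, 0.65 and 0.86 points but keeps its sign.

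**Step 4: other cohort sizes.** Clopper-Pearson half-widths at the stated rates, from the same beta quantiles with x = p·n (non-integer x allowed, so these are interpolations):

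| Evaluable per cohort | 70% | 75% | 80% |
|---|---|---|---|
| 18 | 22.3 | 21.3 | 20.0 |
| 20 | 21.2 | 20.2 | 19.0 |
| 22 | 20.2 | 19.3 | 18.1 |
| 30 | 17.3 | 16.5 | 15.4 |

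On this basis the stated values are first met at 23, 23 and 24 evaluable participants. On the expected-width basis, 22 evaluable give 19.75, 18.79 and 17.54, which essentially meets them. The row for 18 applies only if 60 is the enrolled total and 10% are lost (20 × 0.9 = 18). That is an outer bound, since both documents say 22 per arm are enrolled, screening failures are replaced (Protocol 9.1.1.1), and participants who miss dose 2 stay in the denominator (Protocol 12.3.3, SAP 2.5.3).

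**Step 5: participant numbers.** 3 × 20 = 60 and 3 × 30 = 90, while 3 × 22 = 66. The totals of 60 and 90 therefore fit 20 and 30 per arm, before any allowance for drop-out, but neither document says so.

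**The case against.** The strongest reply is that nothing depends on this sentence. The stated figures are correct for a normal approximation, a usual planning shortcut. The cohort size was set by feasibility, the analysis is descriptive, and the report will contain Clopper-Pearson intervals whatever section 12.6.1 says. Amendment 2 stopped recruitment and the latest SAP revision followed the final data review, so the text can no longer guide a decision on size. A protocol change needs a formal amendment (Protocol 14.1), so it is not cost-free. Read as true rates, the shortfall is roughly half the headline size, and with all 22 enrolled participants evaluable the expected widths essentially reach the stated ones. Finally, 60 can naturally be read as the target before drop-out.

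Most of this stands as an argument about weight: the effect is small and the cohort size need not change. It does not remove the inconsistency. The sentence is written for 20 participants, is not labelled an approximation, and sits in documents that commit to the exact method. On either reading of the response rate, the exact interval at 20 is wider than stated at all three rates. The reading of 60 as a pre-drop-out target is plausible, but it is not written down.

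**Conclusion.** The concern holds. The half-widths in Protocol 12.6.1 and SAP section 3 belong to a Wald interval and not to the planned one. At n = 20 they are too small by 1.1, 1.2 and 1.5 points at observed rates of 70%, 75% and 80%, or by about 0.5 to 0.9 points if averaged over the binomial. That the method was Wald is inferred from the match of all three figures, since neither document names it. The exact limits follow directly from the plan's own n, rates and interval.

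This is a correction to the stated precision. It does not challenge the sample size or the analysis, and no reported result changes. The question of 60 against 66 participants is a secondary gap in wording.

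**What to change.** In SAP section 3 and Protocol 12.6.1, replace the margin-of-error sentence with: *With 20 evaluable participants, the exact Clopper-Pearson 95% confidence intervals are 45.7–88.1%, 50.9–91.3% and 56.3–94.3% for observed rates of 70%, 75% and 80% (half-widths 21.2, 20.2 and 19.0 percentage points).* Giving the limits also shows the asymmetry. Labelling the present figures as normal-approximation values would remove the contradiction, but would leave the reader without the precision of the reported interval.

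In the same edit, state whether 60 (up to 90) counts enrolled or evaluable participants, given 22 enrolled per arm.

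The cost is wording in two documents, with no change to the sample size, analysis or conduct. The stated precision becomes slightly less favourable. Because the protocol text can change only by written amendment, that part can reasonably go into an amendment made for another reason. The study report should in any case quote the exact figures.
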